5.5 Solicited Safety Set

The Solicited Safety Set consists of all participants in the Safety Set who contribute any solicited AR data, i.e., have at least one post-baseline solicited safety assessment. The Solicited Safety Set will be used for the analyses of solicited ARs and participants will be included in the vaccination group corresponding to the study injection they actually received.

6 Statistical Analysis

6.1 General Considerations

For Phase 1/2, Phase 2 NH, and Phase 2 Extension, the Schedules of Events (SoE) are provided in [Appendix E](#).

General considerations for analyses will be applied to Phase 1/2, Phase 2 NH, and Phase 2 Extension, unless otherwise specified. All analyses will be conducted using SAS Version 9.4 or higher. Statistical outputs (tables, figures, listings, and datasets) will refer study participants as subjects and will use injection of IP and injection interchangeably.

For the summary statistics of all numerical variables unless otherwise specified, the display precision will follow programming standards. Please see [Appendix A](#) for variable display standards.

When count data are presented, the percentage will be suppressed when the count is zero in order to draw attention to the non-zero counts. A row denoted “Missing” will be included in count tabulations where specified on the shells to account for dropouts and missing values. The denominator for all percentages will be the number of participants in that vaccination group within the analysis set of interest, unless otherwise specified.

Continuous variables will be summarized using the following descriptive summary statistics: the number of participants (n), mean, standard deviation (SD), median, minimum (min), and maximum (max).

Categorical variables will be summarized using counts and percentages.

Baseline value is defined as the most recent non-missing measurement (scheduled or unscheduled) collected before injection, unless otherwise specified. For immunogenicity tests and nasopharyngeal (NP) swab tests, the baseline is defined as the most recent non-missing result/measurement (scheduled or unscheduled) collected before or on the date (and time, if available) of injection (Day 1).

Study day relative to injection will be calculated as below:

- Study day prior to injection will be calculated as: date of assessment/event – date of injection.
- Study day on or after the date of injection will be calculated as: date of assessment/event – date of injection + 1.

For calculation regarding antibody levels/titers, antibody values reported as below lower limit of quantification (LLOQ) will be replaced by $0.5 \times \text{LLOQ}$. Values that are greater than the upper limit of quantification (ULOQ) will be converted to the ULOQ. Missing results will not be imputed.

The following **analysis periods for safety analyses** will be used in this study:

- 7 days following vaccination: this period includes the day of vaccination and 6 subsequent days. This analysis period will be used for solicited local and systemic AR that occur during this time.
- Up to 28 days following vaccination: this period starts from the day of vaccination and spans 28 days to include the day of vaccination and 27 subsequent days. This

analysis period will be used as the primary analysis period for safety analyses including unsolicited AE, except for solicited AR, unless specified otherwise.

- Overall period: this analysis period starts on Day 1 and continues through the earliest of the following: study completion, discontinuation from the study, or death.

Unscheduled visits: Unscheduled visit measurements will be included in analysis as follows:

- In scheduled visit windows per specified visit windowing rules.
- In the derivation of baseline/last on-treatment values.
- In the derivation of max/min on-treatment values and max/min change from baseline values for safety analyses.
- In individual participant data listings as appropriate.

Visit windowing rules: The analysis visit windows for protocol-defined visits are provided in [Appendix B](#).

Incomplete/missing data:

- Imputation rules for missing prior/concomitant medications, non-study vaccinations and procedures are provided in [Appendix C](#).
- Imputation rules for missing AE dates are provided in [Appendix D](#).
- For laboratory assessments (Phase 1/2 only), if majority of results are indefinite, imputation of these values will be considered. If the laboratory results are reported as below the LLOQ (e.g., < 0.1), the numeric values will be imputed by $0.5 \times$ LLOQ in the summary. If the laboratory results are reported as greater than the ULOQ (e.g., > 3000), the numeric values will be imputed by ULOQ in the summary.
- Other incomplete/missing data will not be imputed, unless otherwise specified.

6.1.1 Phase 1/2

Age groups:

The following age groups will be used for summary purposes:

- Overall
- Age: ≥ 18 to < 50 years
- Age ≥ 50 years

Vaccination groups:

The following vaccination groups will be used for summary purposes:

- mRNA-1010 50 μg
- mRNA-1010 100 μg
- mRNA-1010 200 μg
- Placebo

For Phase 1/2, all analyses and data summaries/displays will be provided by vaccination group (and then by age group) using appropriate analysis population, unless otherwise specified. Summaries may also contain a display for all mRNA-1010 vaccination groups (Total mRNA-1010 group) or all vaccination groups, including placebo (Overall group).

6.1.2 Phase 2 Northern Hemisphere

Age groups:

The following age groups will be used for summary purposes:

- Overall
- Age: ≥ 18 to < 50 years
- Age ≥ 50 to < 65 years
- Age ≥ 65 years

Vaccination status:

The following previous flu vaccination status may be used for summary purposes:

- Received season flu vaccine in the previous season
- Not received season flu vaccine in the previous season

Vaccination groups:

The following vaccination groups will be used for summary purposes:

- mRNA-1010 25 µg
- mRNA-1010 50 µg
- mRNA-1010 100 µg
- Active comparator

For Phase 2 NH, all analyses and data summaries/displays will be provided by vaccination group (and then by age group) using appropriate analysis population, unless otherwise specified. Summaries may also contain a display for all mRNA-1010 vaccination groups (Total mRNA-1010 group) or all vaccination groups, including active comparator (Overall group). Additional summaries/displays based on vaccination status will be provided for immunogenicity analyses only.

6.1.3 Phase 2 Extension

Age groups:

The following age groups will be used for summary purposes:

- Overall
- Age: ≥ 18 to < 50 years
- Age ≥ 50 years

Vaccination groups:

The following vaccination groups will be used for summary purposes:

- mRNA-1010 6.25 µg
- mRNA-1010 12.5 µg
- mRNA-1010 25 µg
- Active comparator

For Phase 2 Extension, all analyses and data summaries/displays will be provided by vaccination group (and then by age group) using appropriate analysis population, unless otherwise specified. Summaries may also contain a display for all mRNA-1010 vaccination groups (Total mRNA-1010 group) or all vaccination groups, including active comparator (Overall group).

6.2 Background Characteristics

The following description of background characteristics analyses will be applied to Phase 1/2, Phase 2 NH, and Phase 2 Extension, unless otherwise specified.

6.2.1 Participant Disposition

The number and percentage of participants in the following categories will be summarized by vaccination group and then by age group) as defined in [Section 6.1](#) based on Randomization Set:

- Randomization Set
- FAS
- PP Set
- Safety Set
- Solicited Safety Set

The percentage will be based on participants in that vaccination group within the Randomization Set (as randomized).

A summary of reasons for participants who are in the Randomization Set but excluded from PP Set will also be provided.

The number of participants in the following categories will be summarized based on participants screened:

- Number of participants screened
- Number and percentage of screen failure participants and the reason for screen failure

The percentage of participants who screen failed will be based on the number of participants screened. The percentage of participants for each reason for screen failure will be based on the number of participants who screen failed.

The number and percentage of participants in each of the following disposition categories will be summarized by vaccination group (and then by age group) based on the Randomization Set:

- Randomized by site
- Received injection

- Completed study
- Prematurely discontinued the study and the reason for discontinuation

The denominator for all percentages will be the number of participants in the vaccination groups within the Randomized Set.

A participant disposition listing will be provided, including informed consent, participants who completed the study injection schedule, participants who completed study, participants who discontinued from participation in the study, with reasons for discontinuation. A separate listing will be provided for screen failure participants with reasons for screen failure.

For all study parts, a participant who completed the final visit on Day 181 (Month 6), defined as 6 months after the study vaccination on Day 1, is considered to have completed the study.

6.2.2 Demographics

Descriptive statistics will be calculated for the following continuous demographic and baseline characteristics: age (years), weight (kg), height (cm), and body mass index (BMI) (kg/m²). Number and percentage of participants will be provided for categorical variables such as sex, race, and ethnicity. The summaries will be presented by vaccination group (and then by age group) as defined in [Section 6.1](#) based on the FAS, PP Set, and Safety Set. If the Safety Set differs from the Randomization Set (e.g., participants randomized but not received any study vaccination or participants received study vaccination other than the vaccination group they were randomized to), the analysis will also be conducted using the Randomization Set.

For screened failure participants, age (years), as well as sex, race, and ethnicity will be presented in a listing.

In addition, participants who are in the Randomization Set but with any inclusion and exclusion criteria deviation will also be provided in a listing.

6.2.3 Medical History

Medical history data will be coded by system organ class (SOC) and preferred term (PT) using the Medical Dictionary for Regulatory Activities (MedDRA).

The number and percentage of participants with any medical history will be summarized by SOC and PT based on the Safety Set. A participant will be counted only once for multiple events within each SOC and PT. SOCs will be displayed in internationally agreed order. PTs will be displayed in descending order of frequency of Total mRNA-1010 group/Overall group and then alphabetically within SOC.

Medical history data will be presented in a listing.

6.2.4 Prior and Concomitant Medications

Prior and concomitant medications and non-study vaccination will be coded using the World Health Organization drug dictionary (WHODrug Global). The summary of concomitant medications will be based on the Safety Set. Categorization of prior, concomitant, and post medications is summarized in [Appendix C](#) Table 5.

The number and percentage of participants using concomitant medications and non-study vaccination during the 7-day follow-up period (i.e., on the day of injection and the 6 subsequent days) and during the 28-day follow-up period after the injection (i.e., on the day of injection and the 27 subsequent days) will be summarized by vaccination groups (as defined in [Section 6.1](#)) as follows:

- Any concomitant medications and non-study vaccination within 7 days post-injection
- Any concomitant medications and non-study vaccination within 28 days post-injection
- Seasonal influenza vaccine within 28 days post-injection
- Antipyretic or analgesic medication within 28 days post-injection

A summary table of concomitant medications and non-study vaccination that continued or newly received on the date of injection through 28 days post-injection will be provided by PT in descending frequency in the Total mRNA-1010 group.

Medications taken to prevent or treat pain or fever will be collected in the electronic diary (eDiary), and summaries will be provided based on the Solicited Safety Set by vaccination group (and then by age group) as defined in [Section 6.1](#), including within 7 days after injection, beyond 7 days after injection, and any time after injection.

Prior, concomitant, post medications, and non-study vaccination will be presented in a listing. Medications taken to prevent or treat pain or fever will also be presented in a listing.

Concomitant procedures will be presented in a listing.

6.2.5 Study Exposure

Study IP administration data as well as subjects with dosing error will be presented in a listing.

Study duration will be summarized since randomization and since the injection.

6.2.6 Major Protocol Deviations

Major protocol deviations are a subset of protocol deviations that may significantly impact the completeness, accuracy, or reliability of the study data or that may significantly affect a participant's rights, safety, or well-being. Major protocol deviations rules will be developed and finalized before database lock.

The number and percentage of the participants with each major protocol deviation type will be provided by vaccination group (and then by age group) as defined in [Section 6.1](#) based on the Randomization Set.

Major protocol deviations will be presented in a listing.

6.2.7 COVID-19 Impact

A listing will be provided for the impact of coronavirus disease 2019 (COVID-19) on the execution of the study.

6.3 Safety Analysis

The following description of safety analyses will be applied to Phase 1/2, Phase 2 NH, and Phase 2 Extension, unless otherwise specified.

Safety and reactogenicity will be assessed by clinical review of all relevant parameters including solicited ARs (local and systemic), unsolicited AEs (including any clinical safety laboratory abnormalities for Phase 1/2), treatment-related AEs, severe AEs, SAEs, AESIs, MAAEs, AEs leading to withdrawal from study vaccine and/or study participation, vital signs measurement, and physical examination findings. Solicited ARs and unsolicited AEs will be coded by SOC and PT according to MedDRA. AESIs are defined and described in detail in the protocol. The Toxicity Grading Scale for Healthy Adult and Adolescent

Volunteers Enrolled in Preventative Vaccine Clinical Trials (Department of Health and Human Services [DHHS] 2007) is used in this study for solicited ARs as presented in the protocol.

All safety analyses will be based on the Safety Set, except summaries of solicited ARs, which will be based on the Solicited Safety Set. All safety analyses will be provided by vaccination group (and then by age group) unless otherwise specified.

6.3.1 Adverse Events

A treatment-emergent AE (TEAE) is defined as any event occurring during the study not before exposure to study vaccine or any event already present that worsens after exposure to study vaccine. Worsening of a pre-existing condition after vaccination will be reported as a new AE.

AEs will also be evaluated by the investigator for the coexistence of MAAE and/or AESI. MAAE is defined as an AE that leads to an unscheduled visit to a healthcare practitioner. AESI is an AE (serious or nonserious) of scientific and medical concern specific to the Sponsor's product or program, for which ongoing monitoring and immediate notification by the Investigator to the Sponsor are required. All AEs will be coded by SOC and PT using MedDRA.

Unsolicited AEs within 28 days after vaccination will be summarized by vaccination group. SAE, AESI, MAAE, and AE leading to discontinuation from the study up to 28 days after vaccination and overall period will be summarized by vaccination group. See [Section 6.1](#) for definitions of analysis groups and analysis period.

All summary tables (except for the overall summary of AEs) for unsolicited TEAEs will be presented by SOC and/or PT with counts of participants included. SOCs will be displayed in internationally agreed order. PTs will be displayed in descending order of frequency of Total mRNA-1010 group and then alphabetically within SOC. When summarizing the number and percentage of participants with an event, participants with multiple occurrences of the same AE or a continuing AE will be counted once. Participants will be presented according to the highest severity in the summaries by severity, if participants reported multiple events under the same SOC and/or PT.

Percentages will be based upon the number of participants in the Safety Set within each vaccination group.

6.3.1.1 Incidence of Adverse Events

An overall summary of unsolicited TEAEs including the number and percentage of participants who experience the following will be presented:

- Any unsolicited TEAEs
- Any unsolicited serious TEAEs
- Any unsolicited fatal TEAEs
- Any unsolicited medically attended TEAEs
- Any unsolicited treatment-emergent AESI
- Any unsolicited TEAEs leading to discontinuation from participation in the study
- Any unsolicited severe TEAEs

The table will also include number and percentage of participants with unsolicited TEAEs that are treatment-related in each of the above categories.

In addition, separate listings containing individual participant AE data for unsolicited AEs, unsolicited TEAEs leading to discontinuation from participation in the study, SAEs, AESI, and medically attended TEAEs will be provided separately.

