8.4. Safety Definitions and Related Procedures

8.4.1. Adverse Event

An AE is defined as any untoward medical occurrence associated with the use of a drug/vaccine in humans, whether or not considered related to the drug/vaccine.

Events Meeting the Adverse Event Definition

- Exacerbation of a chronic or intermittent pre-existing condition, including an increase in frequency and/or intensity of the condition, after the IP injection.
- New conditions detected or diagnosed after the IP injection even though they may have been present before the start of the study.

Events NOT Meeting the Adverse Event Definition

- Procedures planned before study entry (eg, hospitalization for preplanned surgical procedure).
- Medical or surgical procedure (eg, endoscopy, appendectomy): the condition that leads to the procedure should be the AE.
- Situations in which an untoward medical occurrence did not occur (social and/or convenience admission to a hospital).

An AR is any AE for which there is a reasonable possibility that the vaccine caused the AE ([Section 8.4.3](#)). For the purposes of IND safety reporting, “reasonable possibility” means that there is evidence to suggest a causal relationship between the vaccine and the AE.

An unsolicited AE is any AE reported by the participant that is not specified as a solicited AR in the protocol or is specified as a solicited AR but starts outside the protocol-defined period for reporting solicited ARs (ie, 7 days after vaccine administration).

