3.1 Phase 1/2

3.1.1 Primary Endpoints

The primary safety objectives will be evaluated by the following safety endpoints:

- Frequency and grade of each solicited local and systemic reactogenicity adverse reaction (AR) during a 7-day follow-up period after vaccination.
- Frequency and severity of any unsolicited adverse events (AEs) during the 28-day follow-up period after vaccination.
- Frequency of any serious adverse events (SAEs), AE of special interest (AESI), and medically attended adverse events (MAAEs) from Day 1 to Day 181/end of study (EoS).
- Safety laboratory abnormalities through 7 days after vaccination.

The primary immunogenicity objectives will be evaluated by:

- Geometric mean titer (GMT) and geometric mean fold rise (GMFR) at Day 29 compared with Day 1 (baseline) and percentage of participants with seroconversion, defined as a Day 29 titer $\geq 1:40$ if baseline is $< 1:10$ or a 4-fold or greater rise if baseline is $\geq 1:10$ in anti-hemagglutinin (HA) antibodies measured by hemagglutination inhibition (HAI) assay.

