3.2 Phase 2 Northern Hemisphere and Phase 2 Extension

3.2.1 Primary Endpoints

The primary safety objectives will be evaluated by the following safety endpoints:

- Frequency and grade of each solicited local and systemic reactogenicity ARs during a 7-day follow-up period after vaccination.
- Frequency and severity of any unsolicited AEs during the 28-day follow-up period after vaccination.

- Frequency of any SAEs, AESIs, and MAAEs from Day 1 through Day 181/EoS.

The primary immunogenicity objectives will be evaluated by:

- GMT of anti-HA antibodies at Day 29 as measured by HAI assay.
- Proportion of participants reaching seroconversion at Day 29 as measured by HAI assay. Seroconversion is defined as:
 1. If LLOQ is 1:10, a Day 29 titer \geq 1:40 if baseline is < 1:10 or a 4-fold or greater rise if baseline is \geq 1:10 in anti- HA antibodies measured by HAI assay.
 2. If LLOQ is greater than 1:10 (e.g. 1:14), a Day 29 titer \geq 4 times of LLOQ if baseline is < LLOQ or a 4-fold or greater rise if baseline is \geq LLOQ in anti- HA antibodies measured by HAI assay.

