6.3.1.2 TEAEs by System Organ Class and Preferred Term

The following summary tables of TEAEs will be provided by SOC and PT using frequency counts and percentages (i.e., number and percentage of participants with an event):

- All unsolicited TEAEs
- All unsolicited TEAEs that are treatment-related
- All unsolicited serious TEAEs
- All unsolicited serious TEAEs that are treatment-related
- All unsolicited TEAEs leading to discontinuation from participation in the study
- All unsolicited severe TEAEs
- All unsolicited severe TEAEs that are treatment-related
- All unsolicited treatment-emergent AESI

- All unsolicited medically attended TEAEs
- All unsolicited medically attended TEAEs that are treatment-related

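### The SAP's itemised SAE tables cover unsolicited events only, which is narrower than the any-SAE primary endpoint and protocol Table 15, and the difference is not declared

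*SAP*

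**What the plan says.** SAP 6.3.1 gives the general commitment: "SAE, AESI, MAAE, and AE leading to discontinuation from the study up to 28 days after vaccination and overall period will be summarized". The breakdown is per arm, and no unsolicited qualifier is attached to SAEs or MAAEs.

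The outputs are then itemised. In SAP 6.3.1.1 the overall table is a summary of unsolicited TEAEs. It has a row for "Any unsolicited serious TEAEs", a fatal row limited in the same way, and a row for "Any unsolicited medically attended TEAEs". A closing sentence adds a treatment-related version of every row, again for unsolicited events. In SAP 6.3.1.2 (the section on system organ class and preferred term) the serious-event tables carry the same limit, for example "All unsolicited serious TEAEs that are treatment-related".

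The listings in 6.3.1.1 are worded differently: those for "SAEs, AESI, and medically attended TEAEs will be provided separately", with no unsolicited limit.

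The primary safety endpoint in SAP 3.2.1 is "Frequency of any SAEs, AESIs, and MAAEs from Day 1 through Day 181/EoS". SAP 3.1.1 has the equivalent endpoint for Phase 1/2. Protocol Table 15 lists SAEs and treatment-related SAEs without restriction, but puts the unsolicited qualifier on its MAAE row and on several others. SAP section 7, on changes from the protocol's planned analyses, says not applicable. SAP section 1 says the SAP prevails where its methods differ from the protocol.

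**The concern.** A table limited to unsolicited events cannot report the frequency of any SAE if a solicited reaction can itself be serious, and the protocol provides for exactly that. The events at risk are vaccine-related by the protocol's own rule. They are also the severe end of the reactogenicity profile, on which protocol 4.3 says the 200 µg dose was judged not to meet the sponsor's target.

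If the tables are programmed from the itemised list, the SAE and related-SAE counts by arm could be too low, and the SAE table would not reconcile with the SAE listing in the same report. Because the SAP prevails and declares no change, the narrower version would govern without explanation.

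**Working it through.** The plan states no figure for this point. The check is an inventory, a trace of one event through the planned outputs, and a unit calculation.

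1. **Inventory of SAE outputs.** SAP 6.3.1.1 gives a serious row and its treatment-related counterpart: 2 rows. SAP 6.3.1.2 gives a serious table and a treatment-related serious table: 2 tables. Total 2 + 2 = 4, and all 4 are limited to unsolicited TEAEs. The fatal row and its related counterpart add 2 more, also limited. No unrestricted SAE table is itemised.

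2. **Source of the narrowing.** It comes from the word unsolicited, not from treatment-emergent. Protocol 8.4.15 collects SAEs from the start of product administration, so the treatment-emergent condition removes nothing.

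3. **Can a solicited reaction be an SAE?** Yes. Protocol 8.4.2 includes adverse reactions in its SAE definition. Protocol 8.4.3 says how to record a solicited reaction that meets that definition: in the solicited section of the eCRF.

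4. **Is such an event unsolicited?** Under protocol 8.4.1 a reaction on the solicited list becomes unsolicited only if it is "specified as a solicited AR but starts outside the protocol-defined period for reporting solicited ARs". One that starts in the 7-day window is not.

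5. **Is it treatment-related?** Protocol 8.4.3 and SAP 6.3.2 both treat every solicited reaction as caused by the vaccine.

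6. **Trace of one hospitalised solicited reaction starting on Day 2.**
   - SAE row and SAE table: not counted.
   - Related-SAE row and table: not counted.
   - SAE listing: shown.
   - Solicited tables (SAP 6.3.2): counted by arm and grade, without a seriousness flag.

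   The participant still enters the SAE row if they also had an unsolicited SAE. The related row needs a related one. A given line of the class-and-term tables needs one in the same class or term.

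7. **How far does grade stand in for seriousness?** In protocol Table 13, Grade 4 involves an emergency room visit or hospitalisation for 8 of 11 reactions (injection site pain, axillary swelling, headache, fatigue, myalgia, arthralgia, nausea/vomiting, chills). Erythema, swelling and fever use other criteria. An emergency room visit alone need not be an SAE. Grade 4 is therefore a partial proxy.

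8. **Unit effect of one omitted participant.**
   - Per arm: 1/45 = 2.2%, 1/50 = 2.0%, 1/150 = 0.67%.
   - Total mRNA-1010 column: 1/(3 × 45) = 1/135 = 0.74% in Phase 1/2; 1/(3 × 150) = 1/450 = 0.22% in Phase 2 NH; 1/(3 × 50) = 1/150 = 0.67% in Phase 2 Extension.

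9. **MAAEs.** There are again 2 rows and 2 tables, all limited to unsolicited events, but these agree with the MAAE row of Table 15. The mismatch is inside the protocol: Table 15 is narrower than the endpoint, and narrower than 8.4.3, which records a solicited reaction with a healthcare visit as an MAAE. Protocol 8.4.3 sends that event to the solicited section of the eCRF, while 8.4.4 looks for MAAEs among unsolicited events, so its inclusion depends on where the site enters it.

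**The case against.** Four replies have weight.

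- **SAP 6.3.1 may already cover this.** If its unqualified list means all SAEs, the commitment exists, and 6.3.1.1 and 6.3.1.2 do not call their lists exhaustive. But a reader who takes 6.3.1 as an express promise of unrestricted summaries goes too far. Protocol 9.5.2 has a similar unqualified list, several items of which Table 15 then limits to unsolicited events. Protocol 9.5.2 also has an ambiguous phrase on event counts that could be read as unsolicited SAEs. The firm support is the endpoint wording and Table 15, which leaves its SAE rows open while restricting others.

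- **The MAAE outputs follow the protocol table.** This stands. A reader might infer that all eight SAE and MAAE outputs depart from Table 15 without declaration. Only the SAE half does.

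- **The event stays visible.** This also stands. It is in the SAE listing and in the solicited tables by grade. Protocol 8.4.13 requires SAE reporting through the EDC system, and a serious event not attributable to another cause triggers a pause under protocol 7.1. It would be wrong to infer that serious reactions go undetected. What is missing is the tabulated SAE frequency, which is the endpoint.

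- **Omission depends on data structure.** Protocol 8.4.3 requires entry in the solicited section but does not bar a parallel AE or SAE record. Whether programming would class that record as unsolicited depends on the eCRF and table shells, which the reader does not have. Omission is therefore conditional on the tables being built as worded, and the SAP has no rule that prevents it.

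**Conclusion.** The point holds for SAEs and should be fixed. All four itemised SAE outputs, and the fatal rows, are narrower than the primary endpoint and Table 15, do not match the scope of the SAE listing, and are not declared in SAP section 7. Built as itemised, they leave a serious solicited reaction with onset inside the 7-day window out of the SAE and related-SAE counts by arm, subject to the exception for a participant with a qualifying unsolicited SAE.

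The unit effects in the working describe one omitted participant and do not predict that one will occur. The documents give no rate for serious solicited reactions, and no hypothesis test depends on these counts. For MAAEs the point is secondary: the SAP follows Table 15, but both are narrower than the endpoint as worded.

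**What to change.** - **SAE outputs.** In SAP 6.3.1.1 and 6.3.1.2, make the SAE, fatal and treatment-related SAE rows and tables cover any SAE regardless of solicited status, on the Safety Set, for the 28-day and overall periods already named in 6.3.1. Count each participant once per category. Keep the unsolicited-only rows beside them if wanted.

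- **Records.** State which records feed the counts (AE page, Reactogenicity page, SAE report) and give a de-duplication rule for an event entered in more than one place.

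- **MAAEs.** Add an any-MAAE row regardless of solicited status, so that the endpoint is reported as worded, and note the difference from Table 15 in SAP section 7.

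**Cost.** SAP wording, a programmed merge, and extra output for two periods, three study parts and the age groups. No new data collection is evident, but the documents do not show whether the Reactogenicity page carries seriousness or healthcare-visit fields. If it does not, the flags must come from the records behind the planned SAE and MAAE listings. SAE and MAAE percentages may be slightly higher than under the current rows.
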